1.1 Background and rationale

Although most respiratory tract infections, including acute bronchitis, are caused by viruses, 53% of diagnosed patients receive antibiotics in Europe, representing one of the main reasons for prescribing antibiotics in adults. This inappropriate use is a major contributor to resistance to antibiotics and is therefore a global threat to public health. Furthermore, symptomatic treatments used in this indication have not yet shown convincing benefits. Therefore, there are no effective conventional medicines to treat acute bronchitis.

Phytotherapy could be a useful and promising resource for the development of candidate drugs for the treatment of acute bronchitis. A review of the literature identified one plant (*Pelargonium si-doides*), which has a standardized extract, EPs®7630 registered on the market in Switzerland under the name of Kaloba®, that may be effective as a symptomatic treatment in the management of acute bronchitis. The PHYTOBRONCH study aims to investigate the efficacy of Kaloba® in the management of acute bronchitis to find alternatives to the ineffective or inappropriate treatments that are currently used in the management of this disease.

1.2 Objectives

The primary objective is to assess the effectiveness of Kaloba® to treat acute bronchitis compared to usual care to reduce:

- Reduction of symptom severity
- Antibiotics use

Secondary objectives are:

- To assess the incidence of adverse events (AEs) and severe adverse events (SAEs)
- To estimate the proportion of primary care physicians (PCPs) who agree to participate in the study

1.3 Timing of SAP writing

This SAP version was written and finalized before enrollment of participants was finished.

SAP for PHYTOBRONCH	Version of SAP: 1	
Based on template: CTU_STA_TEM-11; v5.0.0	Valid from: 20.03.2025	Page 5 of 15

2. Study Methods

2.1 Trial design

This is a pragmatic, open-label, superiority randomized controlled trial, which takes place in ~40 PCP in practices and 5 walk-in clinics. The intervention group receives Kaloba® for 7 days and up to 21 days. The control group receives usual care, with symptomatic treatments freely chosen by the PCP (phytotherapy excluded). Usual care is not standardized between PCPs. A delayed use of antibiotics can be used in both groups. Prescription of paracetamol is allowed, as well as any routine medication pre-reviewed by the PCP and not counter-indicated.

2.2 Randomization

Participants are randomized in a 1:1 ratio to either the intervention group or the control group, with stratification according to PCP. Randomization was performed using blocks of equal size (size=4). An independent statistician built the randomization table.

Study group allocation is done using the web-based system REDCap (hosted by the University of Fribourg), which also contains the electronic case report form (eCRF). The PCP uses the button "randomize" in REDCap to allocate each patient to a group.

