2.3 Sample size

The sample size was calculated for each of the co-primary outcomes, using a Bonferroni correction for the significance level (.05 / 2 = .025). It was replicated in Stata 18 as follows:

- Reduction of symptom severity: Using a two-sample means test with power = 80%, a two-sided significance level = 2.5%, an allocation ratio 1:1, one day of difference between groups (Δ=1), and a standard deviation of 3 days assumed to be the same in both groups (1), we needed n=346 (173 in each group).
- Antibiotics use: Using a two-sample proportions test (Pearson's chi-squared test) with power = 80%, a two-sided significance level = 2.5%, an allocation ratio 1:1, a proportion of 60% in the control group and 45% in the intervention group (Δ =15) (2), we needed n=420 (210 in each group).

The largest sample size estimation was selected: n=420. As this approach is rather conservative (e.g., it does not consider the fact that the co-primary outcomes may be correlated), we did not account for potential drop-out in the sample size calculation.

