2.8 Blinding

This study is not blinded.

3. Data Management

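### Fixed blocks of four within each PCP, in an unblinded trial, make up to about 29% of allocations certain in advance to a recruiter who knows or infers the block size

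*Combined protocol and SAP*

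**What the plan says.** SAP section 2.2 describes the scheme: "Participants are randomized in a 1:1 ratio to either the intervention group or the control group, with stratification according to PCP". The block size is constant: "Randomization was performed using blocks of equal size (size=4". The list has a protected origin ("An independent statistician built the randomization table"), and the PCP uses a button "in REDCap to allocate each patient to a group", so allocations are released one at a time.

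Section 2.8 adds: "This study is not blinded". Section 2.1 calls the trial open-label and gives its spread: "which takes place in ~40 PCP in practices and 5 walk-in clinics". Section 2.3 sets the size: "The largest sample size estimation was selected: n=420".

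Three other places bear on the point.
- Section 5.2 leaves part of eligibility to the PCP. Inclusion criterion 3b depends on whether the PCP thinks acute bronchitis is the likeliest diagnosis, and exclusion criterion 1 on whether the infection needs antibiotics.
- Section 5.1 states that screening data are not available.
- Section 1.3 places finalization of the SAP before the end of enrolment.

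The SAP mentions neither varying block sizes nor any step to keep the size from PCPs. It does not say that PCPs were told the size.

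**The concern.** Concealment protects a randomized comparison because the recruiter cannot foresee the next arm. Here the stratum is the recruiter, who in a single-physician practice sees every earlier allocation in that stratum. Once two patients in a block of four have gone to one arm, the rest of that block is fixed. An independently built table and one-at-a-time release keep the list itself hidden, but they do not remove this determinism.

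What is at stake is selective enrolment. A PCP who expects a given arm next could apply criterion 3b or exclusion 1 more or less strictly without breaking a written rule. Exclusion 1 bears directly on the antibiotics co-primary outcome. The adjustment set in section 4.3 covers type of recruitment, age, sex, education, smoking, symptom duration, baseline ABSS and corticosteroid prescriptions. It contains no measure of clinical suspicion of bacterial infection. Without screening data, there is no log in which such selection would show.

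**Working it through.** **Inputs.** Block size 4, ratio 1:1, stratum = PCP (section 2.2); no blinding (2.8); about 40 PCPs and 5 walk-in clinics (2.1); N = 420, two-sided alpha 0.025, power 80%, antibiotic use 60% versus 45% (2.3). Assumption: each walk-in clinic is one stratum, giving about 45 strata.

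**Plan's own figure.** The plan gives no figure for predictability. Its sample size reproduces (pooled variance, no continuity correction):

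n per group = [2.2414 × √(2 × 0.525 × 0.475) + 0.8416 × √(0.60 × 0.40 + 0.45 × 0.55)]² / 0.15² = 4.711 / 0.0225 = 209.4, so 210 per group and 420 in total. Nothing below changes this.

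**One complete block.** Six sequences of two A and two B are equally likely. An allocation is forced when earlier ones in the block leave only one arm.

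| Position | P(forced) | P(best guess correct) |
|---|---|---|
| 1 | 0 | 1/2 |
| 2 | 0 | 2/3 |
| 3 | 1/3 | 2/3 |
| 4 | 1 | 1 |

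Forced: 4/3 of 4 = 33.3%. Best guess correct: 17/6 of 4 = 70.8%, against 50% by chance.

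**At the planned size.** 420/45 = 9.3 per stratum, that is 30 strata with 9 patients and 15 with 10. Each has two complete blocks (8/3 forced) plus one or two patients in positions 1 and 2 of a third block (0 forced). Total: 45 × 8/3 = 120, and 120/420 = 28.6%. Simulated random or uneven recruitment over 40 to 45 strata gives about 29% to 30%. With 100 strata (an assumption, for example one per clinic physician) it falls to about 23% to 25%.

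**If the size must be inferred.** After one block, only the second block's forced allocations can still be exploited: 45 × 4/3 = 60, and 60/420 = 14.3%. After two blocks: 0%. Inference is not immediate. Under simple randomization a 2–2 split in the first four patients occurs with probability 6/16 = 37.5%, and balance at both 4 and 8 with (6/16)² = 14%.

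**What selection could do (assumed effects, for illustration only).** Suppose selection alone shifts antibiotic risk between arms by 10 points among the forced 28.6%. Bias = 0.286 × 10 = 2.9 points, against the planned 15. With a common rate of 60%, SE = √(2 × 0.6 × 0.4 / 210) = 4.8 points. The shift is 0.60 SE, and two-sided type I error rises from 2.5% to about 5%. With a 20-point shift it is about 15%. If only a quarter of PCPs exploited a 10-point shift, it is about 2.7%.

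**Effect of varying the blocks.** With sizes 4 and 6 equally likely, and a PCP who knows the possible sizes but not their order, simulation gives about 5% to 6% certain for 9 to 12 patients per stratum. Best-guess accuracy falls less: from about 69% to 66% at 9 patients, and from about 71% to 68% at 12.

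**Power of the retrospective checks.** With 120 forced allocations (60 per arm), the detectable baseline difference at 80% power and two-sided 5% is (1.96 + 0.84) × √(2/60) = 0.51 SD. Excluding them leaves 300 (150 per arm). For 60% versus 45% at alpha 0.025: (0.15 − 2.2414 × √(0.49875/150)) / √(0.4875/150) = (0.15 − 0.1292)/0.0570 = 0.36, a power of about 64%.

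**The case against.** A reader might infer that PCPs did know a third of allocations in advance, or that a short run of patients would be enough to reveal the pattern. The documents support neither. They do not say that PCPs were told the block size, and at about nine patients per stratum, inferring it uses up most of the allocations that could be exploited. The one-third figure also needs complete blocks and a size known from the first patient.

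A reader might also add that the PCP influences antibiotic use after allocation. That is an open-label issue; varying the blocks would not change it, and it is no part of this point.

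Other objections carry weight.
- The stratum in walk-in clinics is not defined. If several physicians share one list, none need see every allocation.
- Selection on recorded baseline variables would appear in the standardized differences planned in section 5.3 and be largely adjusted for, so the main exposure is selection on unrecorded features.
- The reviewed text is a SAP. It refers to a protocol (sections 6.2.4 and 7) that may describe concealment more fully, so silence here is weak evidence.
- How many blocks were still unopened is unknown.

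These limit the size of the concern and the confidence that harm occurred. They do not remove the design weakness: a constant block within the recruiter, no blinding, eligibility that depends on judgement, and no screening data.

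**Conclusion.** The point holds as a conditional weakness of the design. For a PCP who knows the block size from the start and tracks allocations, at most about 29% are certain under even recruitment of 420 over about 45 strata, and 33% in complete blocks. For one who infers the size after the first block the figure is about 14%; after two blocks it is nil. These figures assume that each walk-in clinic is one stratum and that the recruiter sees all earlier allocations in it.

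Selective enrolment is possible and could not be checked from a log. Whether it happened cannot be told from the documents, and its effect on the results could range from negligible to material. The sample size is not affected.

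**What to change.** **If unopened blocks or new sites remain.** Have the independent statistician replace the unused part of the REDCap table with randomly varying block sizes, for example 4 and 6, and keep the sizes out of anything PCPs can see. This is a one-off rebuild. The downside is slightly more imbalance within a PCP, and the gain is small if enrolment is nearly complete. It removes most of the certainty but only a little of the guessability.

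**For allocations already made.** Flag each forced allocation from the table and the order of randomization within stratum. Before database lock, add to the SAP:
- in section 5.3, a comparison by arm of baseline ABSS, age, symptom duration and smoking among the forced allocations;
- in section 6.2.3, a sensitivity analysis of both co-primary outcomes excluding the forced allocations.

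Both use data already collected and cost little programming. State their limits. Power is low, the baseline check cannot detect selection on unrecorded features, and the exclusion leaves second positions, which can still be guessed two times in three.

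**Reporting.** State in section 2.2 whether the block size was withheld from PCPs and how the stratum is defined in walk-in clinics.

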2.3 Sample size

The sample size was calculated for each of the co-primary outcomes, using a Bonferroni correction for the significance level (.05 / 2 = .025). It was replicated in Stata 18 as follows:

- Reduction of symptom severity: Using a two-sample means test with power = 80%, a two-sided significance level = 2.5%, an allocation ratio 1:1, one day of difference between groups (Δ=1), and a standard deviation of 3 days assumed to be the same in both groups (1), we needed n=346 (173 in each group).
- Antibiotics use: Using a two-sample proportions test (Pearson's chi-squared test) with power = 80%, a two-sided significance level = 2.5%, an allocation ratio 1:1, a proportion of 60% in the control group and 45% in the intervention group (Δ =15) (2), we needed n=420 (210 in each group).

The largest sample size estimation was selected: n=420. As this approach is rather conservative (e.g., it does not consider the fact that the co-primary outcomes may be correlated), we did not account for potential drop-out in the sample size calculation.

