4.1 Confidence intervals and *P* values

Statistical tests will be two-sided with a 5% significance level, except for the co-primary outcomes, for which a 2.5% significance level is used. We will present 95% confidence intervals, used to assess the precision of the estimates. We will not calculate p-values for baseline comparisons.

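### Testing each co-primary at a fixed 2.5% is valid but needlessly conservative: Holm's procedure keeps the same 5% family-wise error, never rejects less, and costs no patients

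*Combined protocol and SAP*

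**What the plan says.** Section 2.3 computes a sample size for each co-primary "using a Bonferroni correction for the significance level (.05 / 2 = .025"). For symptom severity it assumes a one-day difference and "a standard deviation of 3 days assumed to be the same in both groups", which gives 346 participants (173 per arm). For antibiotic use it assumes "a proportion of 60% in the control group and 45% in the intervention group", which gives 420 (210 per arm). The larger number is taken. The section acknowledges that the approach is cautious, since it ignores possible correlation between the endpoints, and gives this as the reason for making no allowance for drop-out.

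Section 4.1 carries the split into the analysis. Tests are at 5% "except for the co-primary outcomes, for which a 2.5% significance level is used". The same section plans 95% confidence intervals. No step-down, fixed-sequence or alpha-recycling rule appears anywhere in the SAP.

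**The concern.** Under the fixed rule, each endpoint must reach 2.5% whatever the other one shows. Once one co-primary has been rejected at 2.5%, only one hypothesis is left, and testing it at the full 5% does not raise the family-wise error above 5%. Holm's procedure uses this: the smaller p-value is compared with 0.025 and, only if it is significant, the larger is compared with 0.05. It needs no assumption that Bonferroni does not already make.

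What is at stake is the second claim. Section 1.2 makes both symptom severity and antibiotic use primary objectives. Antibiotic use determines the sample size and sits at its 80% target with nothing in reserve. A p-value between 0.025 and 0.05 for antibiotics, beside a clear symptom result, would count as a failure under the present rule and as a success under Holm.

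**Working it through.** **Inputs (section 2.3).** Two-sided α = 0.025 per endpoint; power 80%; 1:1 allocation; antibiotics 60% v 45%; symptoms Δ = 1 day, SD = 3 days; 210 per arm. The correlation between the endpoints is not given. I take 0 as the base case and show a range.

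**Reproducing the plan's figures.** Antibiotics, with pooled variance under the null and no continuity correction: n per arm = [z(0.9875)·√(2·0.525·0.475) + z(0.80)·√(0.60·0.40 + 0.45·0.55)]² / 0.15² = (2.2414·0.7062 + 0.8416·0.6982)² / 0.0225 = 209.4, so 210 per arm and 420 in total. Symptoms: the t-based calculation gives 173 per arm, 346 in total. Both agree with section 2.3.

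**Power at 210 per arm (normal approximation).**

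- Antibiotics, level α: Φ[(0.15·√210 − z(1−α/2)·0.7062)/0.6982]. At 2.5% this is Φ(0.846) = 0.801; at 5%, Φ(1.131) = 0.871.
- Symptoms, level α: Φ[(1/3)·√(210/2) − z(1−α/2)]. At 2.5% this is Φ(3.416 − 2.241) = 0.880; at 5%, Φ(3.416 − 1.960) = 0.927.

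**Holm, independent endpoints.** An endpoint is rejected if its p ≤ 0.025, or if its p ≤ 0.05 and the other endpoint's p ≤ 0.025.

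- Antibiotics: 0.801 + (0.871 − 0.801)·0.880 = 0.863 (unrounded inputs: 0.8626)
- Symptoms: 0.880 + (0.927 − 0.880)·0.801 = 0.918
- Both: 0.871·0.927 − (0.871 − 0.801)·(0.927 − 0.880) = 0.804
- At least one: 1 − (1 − 0.801)·(1 − 0.880) = 0.976 under either rule, because Holm's first step is Bonferroni

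| | Fixed 2.5% | Holm |
|---|---|---|
| Antibiotics | 80.1% | 86.3% |
| Symptoms | 88.0% | 91.8% |
| Both | 70.5% | 80.4% |
| At least one | 97.6% | 97.6% |

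Simulating the antibiotic test on binomial counts gives 81.3% under the fixed rule and 85.9% under Holm, so the discreteness of the data trims the gain to 4.6 points.

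**Correlation.** From −0.3 to 0.99, Holm power for antibiotics stays between 85.3% and 86.7%. At a correlation of 0.5, the chance of winning on both rises from 74.0% to 82.3%.

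**Smaller true symptom effect (SD 3, independent endpoints).** Holm antibiotic power = 0.801 + 0.070 × symptom power at 2.5%.

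| True symptom effect | Symptom power at 2.5% | Antibiotic power, Holm |
|---|---|---|
| 1 day | 88.0% | 86.3% |
| 0.75 day | 62.6% | 84.5% |
| 0.5 day | 29.7% | 82.2% |
| 0.25 day | 8.3% | 80.7% |
| none | 2.5% | 80.3% |

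**Loss (assumed; the SAP gives no figure).** With 10% loss, treated as 189 complete cases per arm, antibiotic power is 75.4% under the fixed rule and 82.1% under Holm. With 15% loss it is 72.7% and 79.7%.

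**Type I error.** With both nulls true, Holm errs exactly when Bonferroni does: simulated 4.95% at correlation 0 and 3.6% at 0.9. With one null true and the other endpoint at its design effect, independence gives 0.025 + 0.025·0.801 = 4.5% (symptom null true) or 0.025 + 0.025·0.880 = 4.7% (antibiotic null true). It cannot exceed 5%, because a single true null is never tested above 5%.

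**The case against.** The fixed split is valid, prespecified and applied consistently in sections 2.3 and 4.1, and the trial meets its 80% target under that rule. All of this stands. A reader might infer that the plan contains a multiplicity error or misses its stated power. The documents do not support that.

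The 86% is also not unconditional. It needs the symptom endpoint to have its full design effect. Section 6.1 sets participants who never reach the 50% reduction to 22 days. This could push the SD above 3, lower symptom power, and so reduce how often the 5% level is released. The antibiotic gain therefore runs from almost nothing to about 6 points. It is never negative.

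The 10% loss is an illustration. The full analysis set keeps all randomized participants with multiple imputation, and antibiotic use is also asked at three phone calls, so complete cases overstate the damage from missing diaries. Holm is no substitute for a drop-out allowance either: at an assumed 15% loss, antibiotic power is just under 80% even with Holm.

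Fixed levels have two real merits. Each endpoint's verdict stands alone, and the matching simultaneous intervals are simple. The second matters less here, since section 4.1 plans 95% intervals rather than intervals matched to the 2.5% level.

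Finally, Holm presumes that success on either endpoint suffices. The SAP does not say so, although splitting alpha makes sense only on that reading.

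**Conclusion.** The point holds as a free or cheap improvement. Replacing the fixed level by Holm at the same 420 participants adds about 6 points of power for antibiotics, about 4 for symptoms and about 10 for winning on both, with no added type I error. These sizes rest on the section 2.3 effects holding for both endpoints, on independence, and on the simple two-sample tests used for planning rather than the covariate-adjusted models with bootstrapped standard errors in section 6.2.1. Correlation changes the antibiotic figure little; a smaller symptom effect changes it most.

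A reader might also infer that Holm makes a positive trial more likely. It does not: the chance of at least one significant co-primary is identical. The benefit is confined to the second claim.

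**What to change.** In section 4.1, replace the fixed 2.5% level by Holm: test the smaller of the two co-primary p-values at 2.5% and, only if it is significant, the larger at 5%. Three details are needed for the rule to be usable.

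1. **One p-value per endpoint.** Name the full-analysis-set model for E1.1 and E2.1. Section 4.3 lists two adjustment sets (recruitment type alone, and the full covariate list), while section 6.2.1 refers only to the adjusted model and puts the full-analysis and per-protocol sets together under the primary analysis. State which adjustment set is primary.
2. **Success criterion.** State that success on either endpoint supports a claim for that endpoint.
3. **Reporting.** Give Holm-adjusted p-values (twice the smaller p-value, capped at 1; and the greater of that value and the larger p-value) beside the 95% intervals already planned.

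Keep section 2.3 as the sizing basis and note that power under Holm is at least as high. The trial is unblinded (section 2.8), so database lock is too late a limit: adopt the change in a dated SAP version before any outcome data by group are examined. If the protocol carries the fixed rule, record the change in section 7.

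The cost is a few sentences and no patients or data. The one drawback is that simultaneous intervals matching Holm are less simple than those matching Bonferroni, so the 95% intervals should be described as individual intervals.

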2.4 Framework

This is a superiority trial, comparing participants who receive Kaloba® to those who receive usual care.

2.5 Statistical interim analyses and stopping guidance

No interim analysis is planned.

2.6 Timing of final analysis

All outcomes will be analyzed after study completion, once the database is cleaned, validated, and locked.

SAP for PHYTOBRONCH	Version of SAP: 1	
Based on template: CTU_STA_TEM-11; v5.0.0	Valid from: 20.03.2025	Page 6 of 15

2.7 Timing of outcome assessments

Participants answer daily a web-based questionnaire (from day 1 to 21, stopping at symptom resolution) and a phone call at days 4, 8, and 22. A paper version of the questionnaire is also available for participants who are unable to answer online.

2.8 Blinding

This study is not blinded.

3. Data Management

3.1 Data export

The database is hosted in the REDCap database system of University of Fribourg. It will be exported as a CSV file and imported in Stata 18 for analyses. Data will be stored on the server of the University of Bern for analyses.

